10.2 General Statistical Considerations

The following standards will be applied for the analyses unless otherwise specified.

Simple summary statistics (descriptive statistics) for continuous data will be n (number of non-missing observations), mean, median, standard deviation, minimum, and maximum.

The frequency count and percentage will be used to summarize categorical data. Summary statistics will be presented.

Summary statistics for all safety and efficacy variables will be presented.

All data collected will be presented in the by-patient data listings, sorted by site, patient and, where applicable, by study visit.

Change From Baseline (CFB) will be summarized by post-dose time point for efficacy and safety assessments, where Baseline for this Long-Term study is defined as follow:

- **Safety Baseline values (physical exam, ECG, Labs, vitals)**
 - o **Day 0** for patient not randomized in SMA-001 study
 - o **Day 28** for patient randomized in SMA-001 study
 - o If the **screening visit for SMA-002** will be performed on different day from SMA-001 study last visit (i.e. not on Day 0 or Day 28 or on Early termination visit with the full panel of assessments performed), assessments have to be repeated and they will be the baseline values for SMA-002
- **Efficacy Baseline values (QoL)**
 - o **Day 0** for patients that completed SMA-001 study
 - o **Day 0** for patients randomized but that not completed SMA-001 study (for example discontinued on Day 7)
 - o **Day 0** for patients who had QoL for SMA-001 study, however, did not qualify for randomization; however, based on PI discretion, the patient had benefit and were allowed to enrol in the SMA-002 study
 - o **SMA-001 screening** for patients who had QoL performed at Screening visit of the SMA-001 study, and no QoL was performed on Day 0 or thereafter.)

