### 3      SYNOPSIS

TITLE OF STUDY:	Long Term Safety Study of Amifampridine Phosphate in Ambulatory Patients with Spinal Muscular Atrophy (SMA) Type 3
PROTOCOL NUMBER:	SMA-002
STUDY SITES:	Up to 3 sites
PHASE OF DEVELOPMENT:	Phase 2a
STUDY RATIONALE:	
The purpose of this study is to evaluate the long-term safety and tolerability of amifampridine phosphate in ambulatory patients with SMA Type 3 who completed Protocol SMA-001 or, who benefit from the medication but were not meet the criteria enter the double-blind portion of SMA-001.

OBJECTIVES:	
Primary
 
 
• To characterize the long-term safety and tolerability of amifampridine phosphate in patients SMA Type 3
 

Secondary	
 
• To assess the clinical efficacy of amifampridine phosphate over time in patients with SMA Type 3 based on changes in quality of life (QoL)
 

STUDY DESIGN AND PLAN:	
This is a long-term extension study for patients who participated in Protocol SMA-001 where the efficacy and safety of amifampridine was evaluated, in ambulatory patients with SMA Type 3. The planned duration of participation for each patient is approximately 2 years (i.e. until amifampridine is approved by Regulatory Agencies for the treatment of SMA Type 3 or the development program is discontinued for this indication).
 
All patients who have completed study SMA-001 and sign an informed consent may enroll in the long-term study. Those patients who demonstrated benefit after completing the dose titration period but failed to meet the randomization criteria on Day 0 (end of the Run-in period for SMA-001 may also be eligible for this study. The evaluations at the end of participation in Study SMA-001 will as baseline for the Long-Term study.

The optimal dose and schedule for amifampridine from the end of the Run-in Period from Study SMA-001 will initially be used for each patient. The Investigator may adjust the dose of amifampridine during the course of this trial, in order to optimize neuromuscular benefit for the patient. Clinic visits for safety assessment and for evaluation of QoL will be made at Months 3, 6, 9, 12, 15, 21 and 27. Additional visits may occur at the discretion of the Investigator.

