**NUMBER OF PATIENTS PLANNED:**

About 12 SMA Type 3 ambulatory patients will be studied.

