**STATISTICAL METHODS:**

**Sample Size Determination**

The study is not powered with respect to any endpoint, but is a study to assess long term safety and lack of tolerance to the effects of amifampridine on QoL.

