5.1 Study Objectives

The primary objectives of the study is to evaluate the long-term safety and tolerability of amifampridine in patients with SMA Type 3.

The secondary objective of the study is to assess the clinical efficacy of amifampridine phosphate over time in patients with SMA Type 3 based on changes in QoL.

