6.1 Sample Size

This study is not powered with respect to any endpoint and no hypothesis is being tested.

The study will enroll those patients who have completed the SMA-001 study and after all final evaluations for that study have been completed, or those who demonstrated benefit after completing the dose titration period but failed to meet the randomization criteria on Day 0 of SMA-001.

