10.11 Efficacy Analyses

Efficacy will be assessed by changes in QoL over time.

Assessments of efficacy will be performed using the following endpoints:

1. CFB in the INQoL subscales scores:

Symptoms (section 1):

- a) Weakness
- b) Muscle “locking”
- c) Pain
- d) Fatigue
- e) Droopy eyelids
- f) Double vision
- g) Swallowing difficulties

Life domains (section 2):

- a) Activities
- b) Independence

- c) Social relationship
- d) Emotions
- e) Body image

Life domains (section 3):

- a) Perceived treatment effects
- b) Expected treatment effects

Quality of Life

2. CFB in the PEDSQL score (where applicable).

The individual domain scores in INQoL will be calculated using the scoring algorithms outlined in [Appendix 2](#).

Results from INQoL questionnaires and PEDSQL inventory of disease specific symptoms will be summarized with descriptive statistics (n, mean, standard deviation, minimum, median, and maximum) per time point (Months 3, 6, 9, 12, 15, 21 and 27) and CFB, using the Day 0 [in the case where patient completed SMA-001 study, was randomized but not completed SMA-001 study, was not randomized; however based on PI discretion, the patient had benefits and were allowed to enroll in the SMA-002] or the screening visit for the SMA-001 study [in the case where patient had QoL performed at Screening visit of the SMA-001 study, and No QoL was performed on Day 0 or thereafter] response as the baseline level.

The subscales of the INQoL questionnaires will be similarly summarized.

Efficacy analysis will be conducted on ITT_{QOL} analysis set. The efficacy analysis will be descriptive and will be presented on observed data only. Means with standard deviations of INQoL and PEDSQL scores will be also presented.

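### QoL change from baseline pools SMA-001 Day 0 (on-drug) baselines with fallback SMA-001 screening baselines, so the mean shifts by kD/n whenever the fallback is used

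*SAP*

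**What the plan says.** SAP 10.2 lists four cases for the QoL baseline. Three use SMA-001 Day 0: patients who completed SMA-001, patients randomised who did not complete it, and patients not randomised but judged to have benefited. The fourth uses SMA-001 screening "for patients who had QoL performed at Screening visit of the SMA-001 study, and no QoL was performed on Day 0 or thereafter".

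SAP 10.11 states "Efficacy will be assessed by changes in QoL over time" and takes whichever of the two visits applies as the baseline in a single by-visit summary of each INQoL and PEDSQL score. The secondary objective in SAP 5.1 is "to assess the clinical efficacy of amifampridine phosphate over time in patients with SMA Type 3 based on changes in QoL".

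The Protocol Synopsis fixes what Day 0 is. It describes some entrants as having "demonstrated benefit after completing the dose titration period but failed to meet the randomization criteria on Day 0 (end of the Run-in period for SMA-001", and says that each patient starts SMA-002 on the dose found optimal by the end of that Run-in.

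Nothing in the outputs separates the two baselines. SAP 10.4 plans no subgroup analyses. Tables 14.6.1 and 14.6.2 have one set of rows per score, with no split or flag by baseline type, and the plots follow the same layout.

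**The concern.** The two baselines sit on opposite sides of the Run-in. Change from Day 0 starts after titration, so it describes whether QoL is held or lost on continued treatment. Change from SMA-001 screening also contains whatever happened between screening and Day 0, including any initial response to the drug. A mean over both mixes two quantities in a proportion that the plan does not control or report.

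QoL is the study's only efficacy measure, and the Protocol plans that "About 12 SMA Type 3 ambulatory patients will be studied", divided between an adult and a paediatric instrument. At that size one or two patients with a different kind of baseline can move a mean. At stake is the reading of the mean change and its plot: a small gain could be maintained benefit, or it could be carried in by a few screening baselines.

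**Working it through.** The plan has no figure to reproduce, since "This study is not powered with respect to any endpoint and no hypothesis is being tested". The check is the algebra of a mixed baseline, followed by a comparison of the SAP rule with the Protocol.

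**Inputs.** About 12 patients (Protocol Synopsis). Two instruments in separate tables (SAP 9.1.1; Tables 14.6.1 and 14.6.2). The documents do not give:
- k, the number of patients in a table with a screening baseline;
- D, the mean QoL change from SMA-001 screening to Day 0 in those patients;
- the number of patients per instrument; n=6 is assumed, to represent an even split of 12.

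**Formula.** Let m be the mean change since Day 0 over all n patients. A Day 0 patient contributes the change since Day 0; a fallback patient contributes that plus the screening-to-Day 0 change. The pooled mean is therefore m + kD/n. With k/n = f, and D the same in each fallback patient, the mixing also adds D√(f(1−f)) to the SD in quadrature. D and m are written in the direction of benefit.

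**Shift of the pooled mean, kD/n, for assumed D of 5, 10 and 20 points:**

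| n | k | share of D | D=5 | D=10 | D=20 |
|---|---|---|---|---|---|
| 12 | 0 | 0% | 0 | 0 | 0 |
| 12 | 1 | 8.3% | 0.42 | 0.83 | 1.67 |
| 12 | 2 | 16.7% | 0.83 | 1.67 | 3.33 |
| 12 | 3 | 25% | 1.25 | 2.50 | 5.00 |
| 6 | 1 | 16.7% | 0.83 | 1.67 | 3.33 |
| 6 | 2 | 33.3% | 1.67 | 3.33 | 6.67 |
| 6 | 3 | 50% | 2.50 | 5.00 | 10.00 |

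**What the shift can do**, taking D=10 and k=3 as an illustration:
- Sign: if every patient is 2 points worse since Day 0, the n=12 mean is −2 + 3×10/12 = −2 + 2.5 = +0.5.
- Attendance: with m=0 and the three fallback patients retained, the mean is 30/12 = 2.5, then 30/9 = 3.33, then 30/6 = 5.0 as others miss visits. If those three leave, it is 0.
- Spread: at n=12 the added SD term is 10√(0.25×0.75) = 4.33.

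**Comparison with the Protocol.** Table 1 lets screening data come from SMA-001 but has an unavailable assessment repeated. Section 13.1 has any procedure not done in SMA-001 completed before enrolment, lists QoL among those procedures, and names Day 0 as the QoL source for non-randomised patients. Neither reaches back to SMA-001 screening. SAP section 12 states that the planned analyses are unchanged. Under Protocol 15.7 the SAP governs where the two differ, so the fallback is the rule that would be run.

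**The case against.** The strongest reply is that the problem may never arise. If sites follow Protocol Table 1 and 13.1, a missing QoL is repeated at entry. That repeat falls after Day 0, so the fallback is not triggered, k=0, and the summary is a clean change from an on-drug baseline. This stands as a limit on size. It does not remove the point, because the SAP provides for patients with no QoL on Day 0 or later and sends them into the same mean.

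Other replies also limit the point. That SMA-001 screening was drug-free is an inference: the SMA-001 protocol is not available, and earlier use cannot be excluded. The formula does not need it, since D is the screening-to-Day 0 change from any cause. Score direction and scale cannot be checked, because the scoring files are attachments that are not shown; many INQoL items in the listings are coded with higher as worse. The by-patient listings carry test dates, so a careful reader might separate the groups, although no summary does.

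A reader might infer more than the documents support:
- That the efficacy objective cannot be answered at all. This is too strong. The endpoint is descriptive, and the Protocol's own sample-size text says that this "is a study to assess long term safety and lack of tolerance to the effects of amifampridine on QoL", which is a maintenance question that Day 0 baselines can address.
- That non-randomised entrants, admitted for benefit, have an inflated Day 0 QoL that will regress to the mean. This needs benefit to have been judged on QoL. The documents speak of neuromuscular benefit and investigator discretion.
- That the two baselines pull the mean in opposite directions. They do not. A Day 0 baseline contributes no initial response, and only the screening baselines shift the mean.

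**Conclusion.** The point holds in conditional form. SAP 10.2 and 10.11, followed exactly, give a mean QoL change shifted by kD/n whenever at least one patient uses the screening fallback and D is not zero. For n=12 and k=1 to 3 the shift is 8% to 25% of D; for n=6 it is 17% to 50%. The actual size cannot be fixed from the documents. With k=0 there is no harm.

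No test, error rate or sample size is affected. The damage is to interpretation of a descriptive secondary endpoint. Separately, and whatever k turns out to be, the fallback is an undeclared departure from the Protocol's rule for missing assessments. The plan should be corrected before analysis, but this does not threaten the study's primary safety aim.

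**What to change.** In SAP 10.2, 10.11 and Tables 14.6.1 and 14.6.2:
- Restrict the change-from-baseline summary and the mean/SD plots to patients with a Day 0 QoL baseline, and label them as maintenance on treatment. Replace the column heading that now refers to screening.
- Report change from SMA-001 screening in a separate table for patients who have a screening QoL, labelled as uncontrolled change from before the Run-in. If only a few patients have a screening value alone, list them instead.
- Declare the fallback in SAP section 12 as a departure from Protocol Table 1 and 13.1.

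The cost is SAP wording plus one more table or listing. No new data are collected, and the Protocol objective does not need rewriting. The Day 0 table loses the fallback patients, so its n is slightly smaller. The second table may hold few patients, since the documents do not show how many had a QoL at SMA-001 screening.

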10.3 Multiple Comparisons/ Multiplicity

No multiple comparisons are foreseen for this study.

10.4 Examination of Subgroups

No subgroup analyses are foreseen for this study.

10.5 Interim Analysis

There will be no Interim Analysis for this study.

10.6 Final Analysis

All final, planned analyses identified in this SAP will be performed by SPARC Consulting, Milan, Italy on behalf of Catalyst Pharmaceuticals following Sponsor Authorization of this Statistical Analysis Plan, Database Lock, and Sponsor Authorization of Analysis Sets.

10.7 Retests, Unscheduled Visits and Early Termination Data

In general, for by-visit summaries, data recorded at the nominal visit will be presented. Unscheduled measurements will not be included in by-visit summaries.

Listings will include scheduled, unscheduled, and early discontinuation data.

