## 10 INVESTIGATIONAL PLAN

### 10.1 Overall Study Design and Plan

This open label outpatient extension study is designed to evaluate the long-term safety, tolerability of amifampridine in patients diagnosed with SMA Type 3. In addition, evaluation of the effects of amifampridine on the QoL will be made. The study will enroll those patients who have completed the SMA-001 study and after all final evaluations for that study have been completed, or those who demonstrated benefit after completing the dose titration period but failed to meet the randomization criteria on Day 0 of SMA-001.

The duration of participation for each patient is expected to be at least 12 months as patients may continue in the study until amifampridine is approved by Regulatory Agencies or the clinical development of amifampridine is terminated for this indication. In addition to amifampridine, patients will continue to receive previous concomitant medications, as needed.

After a new informed consent is signed and inclusion / exclusion criteria for the current protocol are satisfied, eligible patients will be given the optimal dose and dosing schedule that was identified in the Run-in Period from Protocol SMA-001.

The findings from the physical exam (including vital signs, weight); 12-lead ECG; clinical laboratory test results (including pregnancy testing) and any ongoing adverse events will be used as the baseline for the Long-Term safety evaluation.

The efficacy measurement is QoL which will be completed every 3 or 6 months. Safety and tolerability assessments will be made every 3 or 6 months or more frequently at the discretion of the Investigator. The study will continue until amifampridine is approved by Regulatory Agencies or until development of the product for this indication is halted. The Investigator may alter the dose and dosing frequency during the Long-Term Study as well as schedule additional clinic visits for any reason.

Patients will be seen in the clinic at the end of Months 3, 6, 9, 12, 15, 21 and 27 as detailed in the Schedule of Assessments in [Table 1](#) and Section 13. In between the 3-or 6-month visits, patients may also have telephone/video contact with the site, or unscheduled visits, if needed.

Any unused medication must be returned to the clinic at each visit for drug accountability, and an additional supply will be dispensed.

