#### **10.6.3 Clinical Laboratory Assessments**

Specific visits for obtaining clinical laboratory assessment samples are provided in [Table 1](#) for the tests required by Protocol. The scheduled clinical laboratory tests are listed in Table 2. In brief, clinical laboratory evaluations are to be performed every 3 to 6 months. These tests can be performed more frequently at the discretion of the Investigator.

All abnormal clinical laboratory result pages should be initialed and dated by an Investigator, along with a comment for each abnormal result indicating whether or not it is clinically significant. Any abnormal test results determined to be clinically significant by the Investigator should be repeated (at the Investigator's discretion) until the cause of the abnormality is determined, the value returns to baseline or to within normal limits, or the Investigator determines that the abnormal value is no longer clinically significant.

Each clinically significant laboratory result should be recorded as an AE. The diagnosis, if known, associated with abnormalities in clinical laboratory tests that are considered clinically significant by the Investigator will be recorded on the AE CRF.

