### 15.5 Safety Analysis

Prior to analysis, all AEs will be coded using the MedDRA coding dictionary. Based on these coded terms, TEAEs and SAEs will be summarized using system organ class and preferred terms, as well as by relationship to treatment. All AEs will be listed, regardless of whether they were study treatment related.

Vital signs will be summarized using descriptive statistics (mean, standard deviation, median, minimum, maximum, and number of non-missing observations) by time point. Changes from baseline will also be summarized by post-dose time point.

Clinical laboratory parameters will be summarized using descriptive statistics (mean, standard deviation, median, minimum, maximum, and number of non-missing observations) by time point. Changes from baseline will also be summarized by post-dose time point. In addition, a shift table will be constructed to show the shifts in laboratory results by parameter relative to the normal ranges. The number and percentage of subjects with the following shifts will be presented: normal/normal, normal/low, normal/high, low/low, low/normal, low/high, high/low, high/normal, and high/high. Similar shift tables will also be constructed for physical exam results. ECG results will be summarized in a shift table with the following

	SMA-002	Page 39
---	---------	---------

shifts presented: normal/normal, normal/abnormal, abnormal/normal and abnormal/abnormal. A table of descriptive statistics for QTc will be created.

Additional safety analyses may be performed as described in the Statistical Analysis Plan (SAP) for the study.

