10.12.5 Laboratory Tests

For blood chemistry and hematology, descriptive statistics will be presented for the observed value and CFB by time point. In addition, a shift table will be constructed to show the shifts in laboratory results by parameter relative to the normal ranges. The number and percentage of patients with the following shifts will be presented by time point: normal/normal, normal/low, normal/high, low/low, low/normal, low/high, high/low, high/normal, and high/high. The laboratory parameters to be collected are given below in [Table 3](#).

Table 3 - Clinical Laboratory Tests

Blood Chemistry	Hematology	Urine Tests
Albumin	Hemoglobin	Appearance
Alkaline phosphatase	Hematocrit	Color
ALT (SGPT)	WBC count	pH
AST (SGOT)	RBC count	Specific gravity
Direct bilirubin	Platelet count	Ketones
Total bilirubin	Differential cell count	Protein
BUN		Glucose
Calcium		Bilirubin
Chloride		Nitrite
Total cholesterol		Urobilinogen
CO ₂ or bicarbonate		Blood in urine
Creatine phosphokinase		
Creatinine		
Glucose		
GGT		
LDH		
Phosphorus		
Potassium		
Total protein		
Sodium		
Uric acid		

ALT, alanine aminotransferase; AST, aspartate aminotransferase; BUN, blood urea nitrogen; CO₂, carbon dioxide; GGT, gamma-glutamyl transferase; LDH, lactate dehydrogenase; RBC, red blood cell; SGOT, serum glutamic-oxaloacetic transaminase; SGPT, serum glutamic-pyruvic transaminase; WBC, white blood cell.

Urinalysis parameters will not be included in summary tables.

All laboratory parameters will be listed for all patients.

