Reference Listings: [16.2.7.4.](#)

Programming Note: "Other Body System" is also recorded, but is not included in the above table; it is listed only.

Table 14.1.13. Physical Examination Abnormalities by SOC and PT / SAF

System Organ Class Preferred Term	Statistic	Amifampridine (N=xxx)
No. of patients with at least one abnormality	n (%)	xx (xx.x%)
System Organ Class 1	n (%)	xx (xx.x%)
Preferred Term 1	n (%)	xx (xx.x%)
Preferred Term 2	n (%)	xx (xx.x%)
Preferred Term x	n (%)	xx (xx.x%)
System Organ Class 2	n (%)	xx (xx.x%)
Preferred Term 1	n (%)	xx (xx.x%)
Preferred Term 2	n (%)	xx (xx.x%)
Preferred Term x	n (%)	xx (xx.x%)
System Organ Class x	n (%)	xx (xx.x%)
Preferred Term 1	n (%)	xx (xx.x%)
Preferred Term 2	n (%)	xx (xx.x%)
Preferred Term x	n (%)	xx (xx.x%)

Abnormalities are those reported in the "Physical Examination" form of the eCRF.
Abnormalities were coded using the MedDRA dictionary version 23. Primary System Organ Class and Preferred Term are presented.
Patients are only counted once per SOC and PT.
Patients can have more than one abnormality.
Percentages are calculated on the number of patients (N) in the SAF analysis set.

Source: xxx.sas, Run on ddmmmyyyy

Reference Listings: [16.2.7.4.](#)

Table 14.2.1. Duration of Treatment / SAF

Amifampridine (N=xx)	
Duration of treatment (days)	
n	xx
Mean (SD)	xx.x (xx.xx)
Median	xx.x
Min, Max	xx, xx

Source: xxxx.sas, Run on ddmmmyyyy

Reference Listings: [16.2.5.2.1.](#)

Table 14.2.3. Amifampridine Dosage by Visit / SAF

Visit: Screening	Statistic	Amifampridine (N=xx)
Dose frequency		
3 times per day	n (%)	xx (xx.x)
4 times per day	n (%)	xx (xx.x)
Amifampridine total daily dose (mg)		
	n	xx
	Mean (SD)	xx.x (xx.xx)
	Median	xx.x
	Min, Max	xx, xx

Source: xxx.sas, Run on ddmmmyyyy

Reference Listings: [16.2.5.1.2.](#)

Programming Note: This table will be repeated for all visits (Screening, End of study month 3, End of study month 6, End of study month 9, End of study month 12, End of study month 15, End of study month 21, End of study month 27, EoS, Extra visit).

Table 14.2.4. Treatment Compliance / SAF

	Statistic	Amifampridine (N=xx)
Compliance (%)	n	xx
	Mean (SD)	xx.xx (xx.xxxx)
	Median	xx.xx
	Min, Max	xx.x, xx.x

Compliance is 100%*(Number consumed) / (Number prescribed).

Source: xxx.sas, Run on ddmmmyyyy

Reference Listings: [16.2.5.2.1.](#)

Table 14.3.1. Summary of Treatment Emergent Adverse Events (TEAEs) / SAF

	Statistic	Amifampridine (N=XX)
No. of patients in SAF Population	n	xx

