Values must be presented in SI unit.

Table 14.4.3. Summary of Haematology Shift Result Relative to the Normal Range / SAF

Parameter (Units)	Visit	Screening		
		Low	Normal	High
Haemoglobin (g/L)	Month 3	n	xx	xx
		Low	xx (xx.x)	xx (xx.x)
		Normal	xx (xx.x)	xx (xx.x)
		High	xx (xx.x)	xx (xx.x)
	...	n	xx	xx
		Low	xx (xx.x)	xx (xx.x)
		Normal	xx (xx.x)	xx (xx.x)
		High	xx (xx.x)	xx (xx.x)
	EOS	n	xx	xx
		Low	xx (xx.x)	xx (xx.x)
		Normal	xx (xx.x)	xx (xx.x)
		High	xx (xx.x)	xx (xx.x)

Source: xxx.sas, Run on ddmmmyyyy

Reference Listings: [16.2.6.2.](#)

Programming Notes: Continue for all Haematology parameters.

Table 14.4.4. Summary of Blood Chemistry Shift Result Relative to the Normal Range / SAF

Parameter (Units)	Visit	Screening			
		Low	Normal	High	
AST (U/L)	Month 3	n	xx	xx	xx
		Low	xx (xx.x)	xx (xx.x)	xx (xx.x)
		Normal	xx (xx.x)	xx (xx.x)	xx (xx.x)
		High	xx (xx.x)	xx (xx.x)	xx (xx.x)
...	...	n	xx	xx	xx
		Low	xx (xx.x)	xx (xx.x)	xx (xx.x)
		Normal	xx (xx.x)	xx (xx.x)	xx (xx.x)
		High	xx (xx.x)	xx (xx.x)	xx (xx.x)
EOS	EOS	n	xx	xx	xx
		Low	xx (xx.x)	xx (xx.x)	xx (xx.x)
		Normal	xx (xx.x)	xx (xx.x)	xx (xx.x)
		High	xx (xx.x)	xx (xx.x)	xx (xx.x)

Source: xxx.sas, Run on ddmmmyyyy

Reference Listings: [16.2.6.1.](#)

Programming Notes: Continue for all Blood Chemistry parameters.

Table 14.5.1. Summary of Vital Signs: Systolic Blood Pressure / SAF

Visit	Actual Values					Change from Screening						
	n	Mean	SD	Min	Median	Max	n	Mean	SD	Min	Median	Max
Screening	xx	xx.x	xx.x	xx.x	xx.x	xx.x						
Month 3	xx	xx.x	xx.x	xx.x	xx.x	xx.x	xx	xx.x	xx.x	xx.x	xx.x	xx.x
Month 6	xx	xx.x	xx.x	xx.x	xx.x	xx.x	xx	xx.x	xx.x	xx.x	xx.x	xx.x
Month 9	xx	xx.x	xx.x	xx.x	xx.x	xx.x	xx	xx.x	xx.x	xx.x	xx.x	xx.x
Month 12	xx	xx.x	xx.x	xx.x	xx.x	xx.x	xx	xx.x	xx.x	xx.x	xx.x	xx.x
Month 15	xx	xx.x	xx.x	xx.x	xx.x	xx.x	xx	xx.x	xx.x	xx.x	xx.x	xx.x
Month 21	xx	xx.x	xx.x	xx.x	xx.x	xx.x	xx	xx.x	xx.x	xx.x	xx.x	xx.x
Month 27	xx	xx.x	xx.x	xx.x	xx.x	xx.x	xx	xx.x	xx.x	xx.x	xx.x	xx.x
EOS	xx	xx.x	xx.x	xx.x	xx.x	xx.x	xx	xx.x	xx.x	xx.x	xx.x	xx.x

Change from Baseline includes only those patients with both a Baseline value and a value for summarized time period.
n represents number of patients contributing to summary statistics.

Source: xxx.sas, Run on ddmmmyyyy

Reference Listings: [16.2.7.2.](#)

Programming Notes: Continue for the following parameters:

- a) Diastolic Blood Pressure (mmHg)
- b) Heart Rate (beats/min)
- c) Respiration Rate (breaths/min)
- d) Body Temperature (°C)
- e) Body weight (Kg)

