Table 14.5.2. 12-Lead ECG / SAF

Statistic	Amifampridine (N=XX)
Screening	xx (x.x)
Normal tracing	n (%) xx (x.x)
Abnormal tracing, NCS	n (%) xx (x.x)
Abnormal tracing, CS	n (%) xx (x.x)
Unknown	n (%) xx (x.x)
Month 3	xx (x.x)
Normal tracing	n (%) xx (x.x)
Abnormal tracing, NCS	n (%) xx (x.x)
Abnormal tracing, CS	n (%) xx (x.x)
Unknown	n (%) xx (x.x)
...	
EOS	xx (x.x)
Normal tracing	n (%) xx (x.x)
Abnormal tracing, NCS	n (%) xx (x.x)
Abnormal tracing, CS	n (%) xx (x.x)
Unknown	n (%) xx (x.x)

CS: Clinically Significant.

NCS: Not Clinically Significant.

Source: xxx.sas, Run on ddmmmyyyy

Reference Listings: [16.2.7.3.](#)

Table 14.5.3. Childbearing Potential and Pregnancy Test / SAF

Visit		Amifampridine	
		Statistic	(N=xx)
Screening	Childbearing potential		
	Patient male	n (%)	xx (xx.x%)
	Menopause	n (%)	xx (xx.x%)
	Sterilized	n (%)	xx (xx.x%)
	Total hysterectomy	n (%)	xx (xx.x%)
	No contraception protection	n (%)	xx (xx.x%)
	Contraception protection	n (%)	xx (xx.x%)
	Child	n (%)	xx (xx.x%)
	Unknown	n (%)	xx (xx.x%)
	Pregnancy test performed?		
	No	n (%)	xx (xx.x%)
	Yes	n (%)	xx (xx.x%)
	Not applicable	n (%)	xx (xx.x%)
	Type of pregnancy test (#)		
	Urine dipstick	n (%)	xx (xx.x%)
	Serum	n (%)	xx (xx.x%)
	Unknown	n (%)	xx (xx.x%)
	Pregnancy test result (#)		
	Negative	n (%)	xx (xx.x%)
	Positive	n (%)	xx (xx.x%)
	Unknown	n (%)	xx (xx.x%)

Percentages are calculated on the number of patients (N) in the SAF analysis set.

Percentages are based on the number of female patients performing pregnancy test.

Source: xxx.sas, Run on ddmmmyyyy

Reference Listings: [16.2.7.1.](#)

Programming Notes: To be repeated for Month 3, Month 6, Month 9, Month 12, Month 15, Month 21, Month 27 and EOS visits.

Table 14.6.1. Summary of INQoL: Weakness / ITT_{QoL}

Visit	Actual Values					Change from Screening						
	n	Mean	SD	Min	Median	Max	n	Mean	SD	Min	Median	Max
Screening	xx	xx.x	xx.x	xx.x	xx.x	xx.x						
Month 3	xx	xx.x	xx.x	xx.x	xx.x	xx.x	xx	xx.x	xx.x	xx.x	xx.x	xx.x
Month 6	xx	xx.x	xx.x	xx.x	xx.x	xx.x	xx	xx.x	xx.x	xx.x	xx.x	xx.x
Month 9	xx	xx.x	xx.x	xx.x	xx.x	xx.x	xx	xx.x	xx.x	xx.x	xx.x	xx.x
Month 12	xx	xx.x	xx.x	xx.x	xx.x	xx.x	xx	xx.x	xx.x	xx.x	xx.x	xx.x
Month 15	xx	xx.x	xx.x	xx.x	xx.x	xx.x	xx	xx.x	xx.x	xx.x	xx.x	xx.x
Month 21	xx	xx.x	xx.x	xx.x	xx.x	xx.x	xx	xx.x	xx.x	xx.x	xx.x	xx.x
Month 27	xx	xx.x	xx.x	xx.x	xx.x	xx.x	xx	xx.x	xx.x	xx.x	xx.x	xx.x
EOS	xx	xx.x	xx.x	xx.x	xx.x	xx.x	xx	xx.x	xx.x	xx.x	xx.x	xx.x

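### The lab shift and ECG tables do not in general show how many patients were ever abnormal; a worst-post-baseline display that includes unscheduled values would close this gap cheaply

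*SAP*

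**What the plan says.** SAP 10.7 bases by-visit summaries on the nominal visit and adds: "Unscheduled measurements will not be included in by-visit summaries". Unscheduled and early-discontinuation data go to the listings. SAP 10.8 rules out visit windowing, so an extra visit near a missed one cannot fill its row.

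For laboratory shifts, SAP 10.12.5 says: "The number and percentage of patients with the following shifts will be presented by time point". The shells follow this. "Table 14.4.3. Summary of Haematology Shift Result Relative to the Normal Range / SAF" and its chemistry counterpart, 14.4.4, run from Month 3 to EOS against the Screening category. The shell "Table 14.5.2. 12-Lead ECG / SAF" gives the tracing category at each visit. No shell for labs, vital signs or ECG has a worst-post-baseline or ever-abnormal row.

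The protocol allows data between visits. Section 10.1 lets the Investigator adjust treatment "as well as schedule additional clinic visits for any reason". Section 10.6.3 says of the laboratory panel: "These tests can be performed more frequently at the discretion of the Investigator". Section 11.3 provides for blood samples after a serious or severe event and at any other time if safety warrants it.

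**The concern.** Safety is the primary endpoint, and a basic question for a safety table is how many patients ever went out of range. Two features of the plan stand in the way.

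- **Unscheduled values.** A result found only at an extra visit or in an event-driven sample enters no lab, vital-sign or ECG summary. After Month 15 the scheduled visits are six months apart, so an extra sample may be the only information in between.
- **No count across visits.** Patients abnormal at different visits are never counted together. Even if no unscheduled sample is ever taken, the visit rows do not generally fix the number of patients ever abnormal.

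The descriptive tables (14.4.1, 14.4.2, 14.5.1) are less affected. Their row minima and maxima show the extreme scheduled value, so only unscheduled values are missing there.

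**Working it through.** The plan states no figure to reproduce: the study is not powered and tests no hypothesis (Protocol 15.6).

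**Inputs.** N = 12 planned patients (Protocol Synopsis); V = 7 scheduled post-baseline visits (Protocol 10.1), plus an EOS row in the shells; 21 chemistry and 10 haematology parameters, with the differential as five cell types (SAP Tables 3 and 4). For simplicity, all 12 patients are taken as normal at baseline and observed at every visit.

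**1. What the visit rows identify.** Let x_v be the number high at visit v, and E the number high at one or more scheduled visits. Then

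max(x_v) ≤ E ≤ min(N, Σ x_v).

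- One patient high in each of 7 rows: 1 ≤ E ≤ 7, that is 1/12 = 8.3% to 7/12 = 58.3%. If the EOS row also shows one patient, the upper bound is 8/12 = 66.7%.
- Two patients high in each of 7 rows: 2 ≤ E ≤ min(12, 14) = 12, that is 16.7% to 100%.
- Three different patients, each high at one different visit: three rows each show 8.3%, while E = 3/12 = 25.0%.
- No row, or only one row, with any abnormality: the bounds meet and the table gives E exactly.

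**2. Unscheduled-only abnormalities.** Each such patient removes 1/12 = 8.3 percentage points from the tables. With one such patient and no other, the rows show 0/12 (exact 95% interval 0 to 26.5%; upper limit 1 − 0.025^(1/12) = 0.265). The data hold 1/12 (0.2% to 38.5%).

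**3. Illustration of the visit effect.** The documents give no rate of abnormal results, so assume an average of 1/12 per visit over 7 visits and a beta-binomial with within-patient correlation ρ. The share ever abnormal is then:

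| ρ | Ever abnormal |
|---|---|
| 0.8 | 12% |
| 0.5 | 20% |
| 0.2 | 31% |
| 0 | 1 − (11/12)^7 = 46% |

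The same per-visit rate of 8.3% fits all four.

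**4. Side effect of a worst-value count.** Suppose each normal result exceeds a given limit by chance with probability 2.5%, independently (assumption). Then 1 − 0.975^7 = 16% of patients exceed it at least once in 7 samples, and 1 − 0.975^11 = 24% in 11.

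**5. Output cost.** Present shift panels: 31 parameters × 8 rows (7 visits plus EOS) = 248. A lowest and a highest panel per parameter: 2 × 31 = 62. Increase: 62/248 = 25%.

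**The case against.** The strongest reply is that nothing promised is missing. A reader might infer that the SAP narrowed the protocol, because Protocol 15.5 says "The number and percentage of subjects with the following shifts will be presented: normal/normal" without naming visits and the SAP adds the time point. The documents do not support that. Protocol 15.3 defines the primary endpoint at Months 3 to 27, and 15.5 summarises lab values by time point just before the shift table. By-visit shifts fit the protocol, and keeping retests out of visit rows is not wrong in itself.

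A reader might also infer that safety signals are lost, since Protocol 8.2 names abnormal liver enzymes and QTc prolongation among the events already reported. That goes too far. Clinically significant changes are recorded as adverse events (Protocol 10.6.2, 10.6.3, 10.6.5, 10.6.6), and SAP 10.12.1 counts each patient once per preferred term. For such changes a per-patient count already exists, although it depends on the Investigator's judgement of significance. All values are listed, and with about 12 patients a hand count is feasible, though no rule for it is written down.

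Nor is there a clean precedent in the SAP. The Table 14.1.13 shell has a row "No. of patients with at least one abnormality" for physical examination and shows no visit rows. But the governing text in SAP 10.12.4 refers to each clinic visit, and the shell is not limited to post-baseline findings.

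Finally, the bounds above are constructed cases, and a worst-value count partly reflects how often a patient is sampled. Both points stand. They limit the size of the concern but do not supply the missing count.

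**Conclusion.** This is a cheap improvement to the primary safety summary, not the correction of an error. The lab shift and ECG tables do not in general identify the number of patients ever abnormal, and abnormalities found only in unscheduled samples appear in no lab, vital-sign or ECG table. The remaining gap is mainly in findings judged not clinically significant and in the size of unscheduled values.

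The possible size is large relative to 12 patients: 8.3% to 58.3% when one patient is high in each of seven rows, and 8.3 points for each patient abnormal only in an unscheduled sample. How often either happens is unknown, because the documents give no rate of abnormal results or extra samples. The bounds assume 12 patients, all normal at baseline and all observed; the correlation and chance-exceedance figures are illustrations under stated assumptions.

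**What to change.** Keep the nominal-visit rows. State an exception in SAP 10.7 for worst-post-baseline displays, which use all scheduled, unscheduled and end-of-study or early-termination values:

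- **Tables 14.4.3 and 14.4.4:** lowest and highest post-baseline category, by baseline category.
- **Tables 14.4.1, 14.4.2 and 14.5.1:** minimum and maximum post-baseline value and change from baseline.
- **Table 14.5.2:** worst tracing category, by baseline category. This gives no QTc value and should not be presented as covering QTc.
- **Beside each:** the number of post-baseline samples per patient (median and range).

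The cost is SAP wording and programming on data already collected, with about 25% more shift output (62 panels on 248) and a few rows elsewhere. Visits and data collection do not change. The drawback is that worst-value counts rise with sampling (16% of patients at 7 samples and 24% at 11 under the 2.5% assumption), so the new rows should be read beside the visit rows and the sample counts.
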